Qualified **currently treated subjects** will be eligible for randomization after the Washout/Placebo Run-in if their seDBP is \geq 95th percentile for age, gender, and height or \geq 90th percentile for age, gender, height if chronic renal disease, diabetes, heart failure or hypertensive target organ damage is present. If a subject's seDBP remains <95th percentile for age, gender, and height or <90th percentile if chronic renal disease, diabetes, heart failure or hypertensive target organ damage is present after the Washout/Placebo Run-in, the washout may be extended in 1 week increments up to 2 times, for a maximum possible washout of 4 weeks, as long as seated systolic blood pressure (seSBP) also remains below this threshold. Placebo should be continued during the extension(s). Subjects whose seDBP remains below the entry criteria after the extensions will not be eligible for randomization to the double-blind treatment phase and shall be discontinued from the study and referred back to their treating physicians to resume appropriate antihypertensive treatment.

Qualified **currently untreated subjects** will have their BP assessed on 3 occasions prior to randomization including Day -1 (or Day 1 for subjects not participating in ABPM). (The initial 2 assessments may occur at Visit 1/Day -28 and Visit 2/Day -14 or as determined by the investigator). The average seDBP at each of these 3 visits must be \geq 95th percentile for age, gender, and height or \geq 90th percentile for age, gender, height if chronic renal disease, diabetes, heart failure or hypertensive target organ damage is present to be eligible for randomization.

Eligible subjects will be randomized into 1 of 4 double-blind treatment arms using an interactive (voice/web) response system (IVRS/IWRS). The 4 treatment groups include (1) low-dose AZM (AZM-L), (2) intermediate-dose AZM (AZM-M) or (3) high-dose AZM (AZM-H) or (4) losartan.

The dose taken by each subject will be dependent on treatment assignment. Subjects assigned to AZM-M, AZM-H or

losartan will initiate treatment at a low dose that will be force-titrated at Week 2 to the final randomized dose, which will be maintained for the final 4 weeks of the DB Phase. In the Withdrawal Phase, subjects will be re-randomized using IVRS/IWRS to continue receiving their previously assigned active treatment or placebo.

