6.0 STUDY DESIGN AND DESCRIPTION

6.1 Study Design

AR14.001 is a global phase 3, efficacy and safety study of AZM in children aged 6 to <18 years with primary or secondary hypertension. At least 213 subjects will participate in a 6-week, double-blind, randomized, treatment phase (DB Phase), followed by a 2-week, double-blind, randomized placebo-controlled withdrawal (Withdrawal Phase). In the DB Phase, subjects will be randomized (1:1:1:1) with AZM (high, intermediate, or low) using 4 doses (10, 20, 40, and 80 mg) or losartan. In the Withdrawal Phase, subjects will be randomized (1:1) to continue taking their previously assigned active treatment or to be switched to placebo. This study also includes a 44-week, OL extension (OL Phase) in which all subjects will receive AZM and other antihypertensive medications (if needed) according to a titrate-to-target BP algorithm. The study will be conducted at approximately 120 sites. BP will be assessed in the clinic throughout the study, and subjects may also participate in a 24-hour ABPM procedure at Baseline, at the end the DB Phase and at the end of the OL Phase.

A schematic of the study design is included as [Figure 6.a](#). A schedule of study procedures is listed in [Section 9.b](#).

Figure 6.a Schematic of Study Design

AZM-L=low-dose AZM, AZM-M=intermediate-dose AZM, AZM-H=high-dose AZM, RZ=Randomization, D=Day, W=Week.

(a) β -blocker use should be tapered off gradually during the first week of the washout. If seDBP remains below inclusion criterion #4 (Section 7.1) after the washout, it can be extended in 1-week increments up to 2 times, for a maximum washout of 4 weeks (for currently treated subjects only). Placebo should continue during the extension(s).

(b) All subjects randomized to AZM-M, AZM-H or losartan will be force-titrated at Week 2.

(c) If possible, the procedures planned for Week 8 or 52 should be completed at the time of discontinuation for subjects who prematurely withdraw from double-blind or OL treatment, respectively.

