6.1.2 Screening and Washout/Placebo Run-in Phase

The duration of Screening can be a maximum of 2 weeks. After clinical laboratory tests results are available and eligibility criteria have been verified (except inclusion criterion #4 and exclusion criterion #6 [[Section 7.0](#)]) qualified subjects will enter a 2-week, single-blind, placebo run-in period, with the first dose to be dispensed in the clinic. For currently treated subjects, the placebo run-in will also serve as a washout period, and antihypertensive medications will be discontinued at Visit 2; however, β -blockers (BBs) should be tapered off gradually during the first week of the washout. Therefore, all currently treated subjects will have a minimum of 7 drug-free days prior to their qualifying clinic seDBP assessment and subsequent randomization.

Qualified **currently treated subjects** will be eligible for randomization after the Washout/Placebo Run-in if their seDBP is \geq 95th percentile for age, gender, and height or \geq 90th percentile by age, gender, height if chronic renal disease, diabetes, heart failure or hypertensive target organ damage is present (ie, inclusion criterion #4 is satisfied) according to percentiles published in the US NHLBI Fourth Report on the Diagnosis, Evaluation, and Treatment of High Blood Pressure in Children and Adolescents [5]. If a subject's seDBP remains $<$ 95th percentile for age, gender, and height or $<$ 90th percentile by age, gender, height if chronic renal disease, diabetes, heart failure or hypertensive target organ damage is present after the Washout/Placebo Run-in (ie, does not satisfy inclusion criterion #4), the washout may be extended in 1 week increments up to 2 times, for a maximum possible washout of 4 weeks, as long as seSBP also remains below this threshold. Placebo should be continued during the extension(s). Subjects whose seDBP remains below the entry criteria after the extensions will not be eligible for randomization to the double-blind treatment phase and shall be discontinued from the study as a run-in failure and referred back to their treating physicians to resume appropriate antihypertensive treatment.

Qualified **currently untreated subjects** will have their BP assessed on 3 occasions prior to randomization including Day -1 (or Day 1 for subjects not participating in ABPM). (The initial 2 assessments may occur at Visit 1/Day -28 and Visit 2/Day -14 or as determined by the

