6.1.4 Double-Blind, Randomized Treatment Phases

6.1.4.1 Double-Blind Phase

Qualified subjects who meet the BP entry requirements (ie, seDBP ≥ 95 th percentile for age, gender, and height or ≥ 90 th percentile for age, gender, height if chronic renal disease, diabetes, heart failure or hypertensive target organ damage is present), including at Day -1/Visit 3 (or Day 1 for subjects not participating in ABPM) will be eligible for randomization. Currently treated subjects who have washed out of their antihypertensive medications but have a BP that remains

below the entry criteria at Day -1 (or Day 1 for subjects not participating in ABPM) may extend the Washout/Run-in Period as described in [Section 6.1.2](#) as long as SBP also remains below the same threshold.

After a qualifying clinic seDBP has been confirmed and anthropomorphic measurements have been recorded, subjects who agree to participate in the ABPM procedure will be fitted with an ABPM device that will be worn for at least 24 hours. After the ABPM device is removed on Day 1/Visit 4, pretreatment vital signs and a full panel of clinical laboratory tests will be completed. Subjects who do not participate in the ABPM procedure will not visit the clinic on Day -1; for these subjects, the qualifying seDBP will be confirmed on Day 1 before randomization.

After the baseline procedures are conducted on Day1/Visit 4, all qualifying subjects will receive their first dose of randomized, double-blind study medication at the investigative site, and study medication will be dispensed. Study medication will be administered orally with water, at an agreed upon (by the site and subject) consistent time of day, with or without food, and will be administered in the clinic on days when a visit is scheduled.

Additional clinic visits will be scheduled at Weeks 2, 4, and 6 of the DB Phase. A renal subpanel (sodium, potassium, chloride, blood urea nitrogen [BUN], creatinine, cystatin C, estimated glomerular filtration rate [eGFR]) will be collected at Week 4/Visit 6, which corresponds to 2 weeks after study drug is force-titrated. The renal subpanel may be completed at an earlier unscheduled visit (ie, 5 to 7 days after Week 2/Visit 5) at the investigator's discretion.

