6.2.3 Use of Placebo

Exposure to placebo will be restricted to the Washout/Placebo Run-in and the Withdrawal Phase. The standard duration of the Washout/Placebo Run-in is 2 weeks, although subjects whose BP remains controlled (ie, seDBP and seSBP <95th percentile or <90th percentile if chronic renal

CONFIDENTIAL

disease, diabetes, heart failure or hypertensive target organ damage is present) after the washout and therefore do not qualify for randomization, may have the washout extended in 1-week increments for up to 2 additional weeks. The purpose of the Washout/Placebo Run-in is to establish a treatment-free baseline BP, as well as to reduce the influence of the placebo effect, prior to initiation of double-blind treatment. In addition, the run-in allows the opportunity to assess subject compliance with study medication (ie, placebo), and subjects who are not sufficiently compliant with single-blind placebo (ie, >130% or <70%) will not qualify for randomization.

In the Withdrawal Phase, half of the subjects will be randomized to receive 2 weeks of placebo treatment, while the other half will continue their current active treatment. The purpose of the randomized, placebo-controlled withdrawal is to allow for direct comparison between AZM and placebo, thereby facilitating estimation of a placebo-adjusted treatment effect for AZM.

Together, the maximum cumulative duration in which an uncontrolled subject may be untreated is 4 weeks, which will be divided into 2 non-consecutive phases. This maximum duration of exposure to placebo is regarded as safe based on meta-analysis of AE and SAE data from 10 pediatric hypertension trials that incorporated a 2 to 4 week, placebo treatment period [22]. Similarly, meta-analysis of safety data from adult hypertension trials indicated that short-term exposure to placebo (usually 4 to 8 weeks) did not increase risk of cardiovascular events relative to active therapy [23]. At any point of the study, a subject whose BP becomes elevated to greater than 15/10 mm Hg above the 99th percentile and is confirmed on repeat test will be discontinued.

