- ABPM devices: Devices will be returned to the site by the subject after each use. After study completion the site will return the devices to Arbor or designee.
- Clinic BP monitoring devices: Instructions on final disposition of the devices will be provided to the sites during the study.
- HBPM devices: Instructions on final disposition of the devices will be provided to the sites during the study.
- BP diary: Diary should be returned to the site by the subject at each OL study visit.

8.1.1.4 *Sponsor-Supplied Drug*

Sponsor-supplied drugs referenced in other sections of the protocol include the following:

- AZM 10 mg, 20 mg, 40 mg, 80 mg, or matching placebo orally administered tablets.
- O/E losartan 25 mg, 50 mg, 100 mg, or matching placebo orally administered capsules.

8.1.2 **Storage**

AZM and matching placebo investigational study drugs should be stored at 25°C (77°F); with excursions permitted to 15°C to 30°C (59°F-86°F). Study medication is to remain stored in the original container until time of dosing.

O/E losartan and matching placebo study drug should be stored at 25°C (77°F); with excursions permitted to 15°C to 30°C (59°F-86°F). Keep container tightly closed. Protect from light. Study medication is to remain stored in the original container until time of dosing.

All clinical trial material must be kept in an appropriate, limited-access, secure place until it is used or returned to the sponsor or designee for destruction. All sponsor-supplied drugs must be stored under the conditions specified on the label, and remain in the original container until dispensed. A daily temperature log of the drug storage area must be maintained every working day. Temperature excursions must be reported to sponsor or designee.

8.1.3 **Dose and Regimen**

Each subject who qualifies following the initial screening visit will enter the 2-week, single-blind placebo Run-in/Washout at Day -14 (Visit 2) and will be dispensed 1 blister card containing AZM placebo tablets and 1 bottle containing losartan placebo capsules. Subjects will receive their first dose of investigational study medication in the clinic. For currently treated subjects, if seDBP remains below inclusion criterion #4 after the Run-in/Washout, it can be extended in 1-week increments up to 2 times, for a maximum washout of 4 weeks. The date of the first dose of single-blind, placebo run-in investigational medication should be recorded in the subject's source document and eCRF.

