Note: X₁=all subjects, X₁=subjects who participate in ABPM, and X₀=subjects who do not participate in ABPM. Only subjects undergoing ABPM should attend visits D-1, W6-1D, and W52-1D (shaded columns).

RZ=Randomization, WD=Withdrawal, OL=Open-Label, D=Day, W=Week, PTE=pretreatment event, AE=adverse event, PK=pharmacokinetics, ICF=informed consent form, HTN=hypertension, SB=single-blind, DB=double-blind.

- (a) Conduct W8 procedures for subjects who prematurely discontinue DB treatment in the DB Phase or WD Phase.
- (b) An additional unscheduled visit may be requested before Week 12 at the investigator's discretion.
- (c) For subjects whose BP is controlled and medications remain unchanged at Week 12, subsequent visits will be scheduled at 8-week intervals. If further medication adjustment is needed, the subject will be required to return to the site for a vital sign evaluation at an unscheduled visit 2 to 4 weeks after each change until medications are stable; a renal subpanel may be requested and/or the visits may occur earlier if deemed necessary. Other unscheduled visits may be requested by the investigator at any time for other reasons; however, if the visit results in a medication change, the up- or down-titration must be registered in IVRS/IWRS.
- (d) Conduct W52 procedures for subjects who prematurely discontinue open-label treatment in the OL Phase.
- (e) Washout/Placebo Run-in visits should be timed so that a subject receives placebo for 14 (± 5) days, unless an extended washout is needed as described in footnote (g).
- (f) Inclusion criterion #4 (ie, seDBP \geq 95th percentile for age, gender, and height or \geq 90th percentile by age, gender, height if chronic renal disease, diabetes, heart failure or hypertensive target organ damage is present) and exclusion criterion #6 (compliance $>130\%$ or $<70\%$) must be confirmed.
- (g) If seDBP remains below inclusion criterion #4, the washout can be extended in 1-week increments up to 2 times (currently treated subjects only), for a maximum washout of 4 weeks. Placebo should be re-dispensed and continued during the extension(s).

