9.3.3.2 Run-in, Day -1 (Visit 3)

This visit will only be required for subjects participating in the ABPM procedure. All other subjects will be assessed at Visit 4. See [Section 9.3.4](#).

Procedures to be completed at Day -1/Visit 3 include:

- Vital signs (including standing measurements) (mean clinic seated DBP must be \geq 95th percentile by age, gender, and height or \geq 90th percentile by age, gender, height if chronic renal disease, diabetes, heart failure or hypertensive target organ damage is present for the ABPM to be initiated).
- Weight and height.
- Concomitant medications.
- AE assessment.
- Collection of single-blind placebo run-in study medication and assessment of subject compliance with dosing. If required, counsel subject or parent/legal guardian on compliance. (See [Exclusion Criterion 6](#))
- Inclusion/exclusion criteria.
- In-clinic dose with single-blind placebo run-in study medication.
- Initiation of 24-hour ABPM immediately after dosing.
- Re-dispensing of placebo single-blind study medication.

If a subject's seDBP remains $<$ 95th percentile for age, gender, and height or $<$ 90th percentile by age, gender, height if chronic renal disease, diabetes, heart failure or hypertensive target organ damage is present after Washout/Placebo Run-in (ie, does not satisfy inclusion criterion #4 on Day -1), the washout may be extended in 1-week increments up to 2 times, for a maximum possible washout of 4 weeks (currently treated subjects only), as long as SBP also remains below this threshold. Placebo should be continued during the extension(s). Subjects whose seDBP remains $<$ 95th percentile or $<$ 90th percentile if chronic renal disease, diabetes, heart failure or hypertensive target organ damage is present after the extensions will not be eligible for randomization to the DB Phase and shall be discontinued from the study and referred back to their treating physicians to resume appropriate antihypertensive treatment.

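### The rule for extending the placebo washout carries a systolic condition in six places in the protocol but not in Figure 6.a, Section 8.1.3, Table 9.b or the SAP's copy of the figure note; the passages need to be reconciled.

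*Protocol*

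**What the plan says.** The entry criterion is diastolic (inclusion criterion 4: seDBP at or above the 95th percentile, or the 90th with listed comorbidities). A currently treated child who falls short after the two-week washout may have it extended by one week, up to twice. The protocol states the condition for doing so in different ways.

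With a systolic condition:
- Study Summary (2.0): "for a maximum possible washout of 4 weeks, as long as seated systolic blood pressure (seSBP) also remains below this threshold".
- Section 6.1.2: "for a maximum possible washout of 4 weeks, as long as seSBP also remains below this threshold".
- Section 6.1.4.1, which refers back to 6.1.2: "as long as SBP also remains below the same threshold".
- Section 6.2.3, which describes extension for "subjects whose BP remains controlled (ie, seDBP and seSBP <95th percentile or <90th percentile if chronic renal" disease or another listed condition is present.
- Section 9.3.3.2 (Day -1/Visit 3): "for a maximum possible washout of 4 weeks (currently treated subjects only), as long as SBP also remains below this threshold".
- Section 9.3.4.1 (Day 1/Visit 4, children not having ABPM): the same condition.

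With diastolic pressure as the only blood pressure condition:
- Figure 6.a note (a), for seDBP still below criterion 4 "after the washout, it can be extended in 1-week increments up to 2 times, for a maximum washout of 4 weeks".
- Section 8.1.3: "if seDBP remains below inclusion criterion #4 after the Run-in/Washout, it can be extended in 1-week increments up to 2 times".
- Table 9.b note (g): "If seDBP remains below inclusion criterion #4, the washout can be extended in 1-week increments up to 2 times (currently treated subjects only").
- SAP Section 3.1, Table A note (a), which repeats the Figure 6.a note.

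The opening text of Section 9.3.3 mentions the extension in a parenthesis within the definition of run-in failure and names no blood pressure condition.

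**The concern.** Take a currently treated child whose seDBP is below the entry threshold after washout and whose seSBP is at or above it. Section 6.1.2 does not allow an extension. The child fails inclusion criterion 4 and leaves as a run-in failure. Section 8.1.3 and Table 9.b note (g), followed as written, allow placebo to continue for one or two more weeks.

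Two things are at stake. The first is placebo exposure in children. Section 6.2.3 defends the use of placebo by stating a maximum untreated time for an uncontrolled subject, and that figure depends on which form of the extension rule is in force. The second is entry: under the shorter form such a child has up to two further chances to reach the diastolic threshold, and under the longer form none. With about 120 sites planned, different sites could act on different statements.

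**Working it through.** No sample size, power or type I error figure is involved. The check compares the texts and adds up nominal weeks.

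**Step 1: can the short statements be followed on their own?** Table 9.b note (g) is worded as a permission and does not refer the reader to Section 6.1.2. Notes (e) and (v) of the same table both point to note (g), and note (v) governs re-dispensing of placebo. Section 8.1.3, the dosing section, gives the same permission. Each therefore reads as a complete instruction without a systolic check.

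**Step 2: reproduce the plan's 4-week figure.** Inputs from Section 6.2.3: standard run-in 2 weeks; Withdrawal Phase placebo 2 weeks; stated maximum untreated time for an uncontrolled subject 4 weeks, divided between two non-consecutive phases.

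Uncontrolled time = run-in + Withdrawal Phase placebo = 2 + 2 = 4 weeks.

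The figure reproduces, but only if extension weeks go to children controlled on both pressures, as Section 6.2.3 describes, so that those weeks do not count as uncontrolled.

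**Step 3: the same sum under the diastolic-only wording.** For a child with low seDBP and raised seSBP, extension weeks count:
- one extension: 2 + 1 + 2 = 5 weeks, 1 week over the stated maximum;
- two extensions: 2 + 2 + 2 = 6 weeks, 2 weeks over.

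The washout alone is then 2 + 2 = 4 weeks. The 6-week total applies only to a child who qualifies on seDBP after the second extension, completes the Double-Blind Phase and is re-randomized to placebo (1:1). These are nominal weeks; Table 9.b note (e) and Section 9.3.3 allow 14 ± 5 days for the standard run-in.

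**Step 4: what bounds the exposure?** Section 7.5 withdraws a child on single-blind treatment whose clinic pressure is confirmed at more than 15/10 mm Hg above the 99th percentile. Table 9.b note (h) repeats this. The inconsistency therefore concerns children with seSBP from the entry threshold (95th percentile, or 90th with comorbidity) up to 15 mm Hg above the 99th percentile.

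**The case against.** The strongest reply is that the short statements are abbreviations. They are silent on systolic pressure, and none says that extension is allowed when it is raised. The full rule is in the Study Summary, in the section that governs run-in, in the placebo justification, and in the instructions for both visits where the extension is decided (Day -1/Visit 3 and Day 1/Visit 4). A site following its visit instructions would meet the condition.

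Much of this stands, and it rules out several stronger readings:
- A reader might infer that the protocol permits a child with raised systolic pressure to be kept on placebo. Taken as a whole it does not; that follows only from relying on a short statement alone.
- A reader might infer that Section 9.3.3 drops the condition. Its opening text is silent, but Section 9.3.3.2 states it.
- A reader might see two deliberate, opposing rules, or assume that Table 9.b outranks the visit sections. The documents show neither an intended second rule nor an order of precedence.
- A reader might infer open-ended untreated hypertension, or a child with no defined disposition. The withdrawal limit bounds the first. For the second, Sections 9.1.14 and 9.3.3 already class a child who has started run-in placebo and is ineligible as a run-in failure.

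The reply does not dispose of the point. Note (g) and Section 8.1.3 are operational text, each worded as a sufficient condition, and note (g) is what the re-dispensing note relies on. The withdrawal limit does not cover the range described in the working.

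**Conclusion.** The point holds as an inconsistency in a safety-relevant rule. Six protocol statements carry the systolic condition. Three protocol statements and one SAP copy give diastolic pressure alone, and one protocol sentence gives no blood pressure condition.

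For a child handled under the short wording, the consequence is up to 2 additional weeks of placebo in the washout and, with Withdrawal Phase placebo, up to 6 nominal weeks against the 4 stated in Section 6.2.3. This assumes that a site acts on the schedule table or dosing section alone, that systolic pressure stays raised but within the withdrawal limit, and, for the 6-week figure, the sequence set out in the working. The documents do not say how many treated children have low seDBP with raised seSBP after washout, so the number affected is unknown.

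No effect on the primary comparison, its power or its type I error has been shown. The correction should be made because the exposure concerns children on placebo and the remedy is cheap.

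**What to change.** Reconcile all the statements of the extension rule to one rule and carry identical wording into Figure 6.a note (a), Section 8.1.3, Table 9.b note (g) and SAP Table A note (a). Have the opening text of Section 9.3.3 refer to that rule. Then confirm that the 4-week statement in Section 6.2.3 holds under the reconciled rule, or restate it.

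Which rule applies is for the sponsor's clinical team. Any IVRS/IWRS check before extension placebo is released should follow the rule they confirm.

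The cost is wording in a protocol amendment and one SAP footnote, plus a system check if the sponsor wants one. No visits or patients are added.
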